### 1.15.4 Datasets

Analyses should be performed on the following datasets as appropriate and as described in the Statistical Analysis Plan:

- *Intent to treat (ITT)*: All randomized subjects who receive at least one dose of the study drug.
- *Per protocol (PP)*: All randomized subjects who have completed the study generally in accordance to protocol, as determined by sponsor. The decision of whether a subject is included in the PP group will be made after all data have been verified and before data analysis.

### 1.15.5 General Principles

Individual subject data will be presented in the data listings. The listings shall include all subjects who were randomized and may exclude all the other subjects.

Summary statistics will be used to describe:

- *Continuous data*: the number of observations (N), mean (mean), standard deviation (SD), median (median), minimum value (min), and maximum value (max). The precision of the measurement unit for each variable will be used to determine the number of decimal places used to report those summary statistics. Min and max will be reported with the same precision. Mean and median will be reported to 1 greater decimal place, and the SD to 2 greater decimal places. Values that require conversion will be converted with the appropriate precision.
- *Categorical data* will be summarized using counts and percentages. Percentages will be presented to 1 decimal place.

Missing or incomplete data will be handled as described in the Statistical Analysis Plan.

### **1.15.6 Demographics and Baseline Characteristics**

Treatment groups will be described and compared with respect to demographics and baseline characteristics (including for example: age, sex, race, weight, height, genotype, phenotype, GA lesion characteristics, microperimetry, smoking status, etc.). The Statistical Analysis Plan will provide details on all analyses.

### **1.15.7 Safety Analyses**

Safety data will be assessed by summarizing the number and proportion of subjects with AEs and the types of AEs, using standard coding. The following are guidelines on how the information will be analyzed. Variations are acceptable, as long as the final report is representative of available data. The Statistical Analysis Plan will provide details on all analyses.

#### *1.15.7.1 Adverse events*

Verbatim terms of AEs recorded by study team will be coded by sponsor using the Medical Dictionary for Regulatory Activities (MedDRA), version 21.0 (most recent version available at the time of the first version of this protocol) or more recent. AEs with onset (or worsening) during the treatment period, i.e. AEs experienced by subjects who have received at least one (1) dose of study drug after randomization will be included in the analysis. AEs recorded prior to the first administration of the study drug or during the run-in period will be considered part of “medical history.”

Summaries, listings, datasets, or subject narratives may be provided, as appropriate, for those subjects who die, interrupt treatment due to an AE, or who experience a SAE.

#### *1.15.7.2 Clinical Laboratory Tests*

Laboratory data will be summarized by analyte. Descriptive statistics will be calculated for selected laboratory analyte at screening and at each scheduled time point.

### **1.15.8 Pharmacokinetic Analyses**

Collection of plasma samples: After venipuncture, blood sample shall preferably be kept on ice until it is spun down and plasma is extracted. Extraction of plasma should occur preferably within one hour of venipuncture. Plasma must be stored at below approximately -20C in amber glass vials and shipped periodically to the bioanalytical lab, as instructed by sponsor or representative. *Details are provided in the bioanalytical manual.*

**Analyses:** The following metabolites of vitamin A (non-deuterated) and ALK-001 (deuterated) will be measured by a bioanalytical lab throughout the study: retinol, retinyl palmitate, retinoic acid. Data will be summarized and presented in plasma absolute concentrations (ng/mL) as well as in % deuterated.

### 1.15.9 Efficacy Analyses

As the primary endpoint, the growth rate of geographic atrophy lesions between baseline and 24 months will be presented. The study is powered to detect a ~33% reduction in the growth rate of atrophy between placebo and ALK-001. The Statistical Analysis Plan (SAP) will provide details on analysis techniques and statistical code. The SAP will be submitted to regulatory authorities before analyses are performed.

## 1.16 ADVERSE EVENTS

### 1.16.1 Definition of Adverse Events

**Definition.** An adverse event (AE) or “Treatment Emergent Adverse Event” (TEAE) is defined as any untoward medical occurrence in a subject that occurs after randomization (V02) or due to the performance of a protocol-specific procedure or assessment, *whether or not it is caused by the study drug*. Medical occurrences that occur prior to V02 or are not due to protocol-specific procedure or assessment will be considered part of medical history.

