#### Examples of AE:

- Observed by study team:
  - o A clinically-significant abnormality in physical or ocular examinations
  - o A clinically-significant finding in ECG, vital signs
- Reported by subject:
  - o A subject-reported new symptom, injury, or disease
  - o A preexisting condition that has worsened (increased in severity, frequency or pattern), unless judged by the investigator as consistent with the natural progression of the preexisting condition.
- Measured in clinical lab:
  - o Deterioration in a laboratory value or other clinical test associated with symptoms or leads to a change in study treatment or concomitant medication (See section [1.16.1.6](#)).

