- AE outcome (see section 1.16.1.14)
- AE causality to study treatment (see section 1.16.1.12)
- Did AE cause subject to withdraw from the study?

*1.16.1.2 Worsening of Geographic Atrophy and AE*  
Events consistent with expected pattern of progression of Geographic Atrophy or AMD should not be recorded as AEs.

Worsening of Geographic Atrophy. Medical occurrences or symptoms of deterioration anticipated as part of normal progression of GA should be recorded as AE only if judged by investigator to have unexpectedly worsened in severity or frequency or changed in nature during the study. When recording an unanticipated worsening of GA, study team should emphasize that condition has unexpectedly changed by including applicable descriptors (eg: “accelerated GA”).

*1.16.1.3 Presence, Development and Worsening of CNV in either eye*

Subjects with Geographic Atrophy are at risk of developing CNV, with a higher risk if one eye has concurrent or a history of CNV. As such:

- Clinical changes in pre-existing CNV consistent with expected progression of CNV should not be recorded as AEs.
- Clinical changes in pre-existing CNV inconsistent with expected progression of CNV should be recorded as AEs.
- Development of CNV in an eye that has no history of CNV should be recorded as AE.

There is no expectation that the study drug would aggravate or accelerate CNV in a subject. As such, treatment with the study drug should continue in case of CNV-related AE.

*1.16.1.4 Preexisting Condition(s) and AE*

Preexisting condition known or discovered at screening or during the run-in period. A preexisting condition is one present prior to or identified during the screening or run-in period, before the first study drug is administered (V02). *Preexisting conditions should be recorded as “Medical History.”*

Clinically-significant abnormality during the screening period. Any clinically-significant abnormality (eg: lab value, ECG, physical exam, etc.) identified during screening or run-in period should be recorded as part of the subject’s medical history.

Preexisting condition discovered during the treatment period. Because patients may sometimes fail to report, or the investigator may fail to detect all preexisting conditions during the screening period, preexisting conditions discovered during the treatment period shall also be recorded as part of the subject’s medical history.

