7.2. Adverse Events and Serious Adverse events

All reported adverse events (AEs) will be coded using MedDRA version 22.0 or higher following the MedDRA Term Selections Points to Consider.

An AE will be considered a treatment-emergent adverse event (TEAE) if it starts on or after the reference start date or if it starts before the reference start date but worsens on or after the reference start date, up to 28 days after last study drug administration.

The overall summary of TEAEs by treatment arm will include the numbers and percentages of subjects with at least one TEAE in the following categories:

- Any TEAE
- TEAE by Maximum Severity (evaluated by the investigator as Mild, Moderate and Severe)
- TEAE related to study drug (evaluated by the investigator as definitely, possibly, probably related)
- Treatment-emergent SAE
- Treatment-emergent SAE related to study drug (evaluated by the investigator as definitely, possibly, probably related)
- TEAE leading to study drug discontinuation
- TEAE leading to study drug interruption
- TEAE leading to study discontinuation
- TEAE leading to death (outcome = “Fatal”)

In addition, the numbers and percentages of subjects with at least one TEAE will be summarized by system organ class (SOC) and preferred term (PT) for the following categories:

- Any TEAE

- TEAE by Maximum Severity (evaluated by the investigator as Mild, Moderate, and Severe)
- TEAE related to study drug (evaluated by the investigator as definitely, possibly, probably related)
- Treatment-emergent SAE
- Treatment-emergent SAE related to study drug (evaluated by the investigator as definitely, possibly, probably related)
- TEAE leading to study drug discontinuation
- TEAE leading to study drug interruption
- TEAE leading to study discontinuation
- TEAE leading to death (outcome = “Fatal”)

Subjects who experienced multiple AEs within the same SOC or PT will only be counted once for that SOC or PT for that level of summarization. The maximum severity will be used in the summary of “TEAE by maximum severity” for subjects who experienced multiple AEs within the same SOC/PT.

Common TEAEs with at least 5% subjects in treatment group ALK-001 or with at least 2% subjects in treatment group ALK-001 and greater than placebo in percentage, will be summarized by PT respectively.

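### Protocol 1.16.1 defines adverse events by two rules that contradict each other, because the medical-history sentence uses 'or' where 'and' is needed

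*Protocol*

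**What the plan says.** The wording is in protocol version 1.1, on which the SAP is based (SAP 1.0). Section 1.16.1 treats AE and TEAE as one term, which covers "any untoward medical occurrence in a subject that occurs after randomization (V02) or due to the performance of a protocol-specific procedure or assessment". It adds that causation by the drug is not required. The sentence that follows reads: "Medical occurrences that occur prior to V02 or are not due to protocol-specific procedure or assessment will be considered part of medical history".

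Other places that sort events into one category or the other:

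- **Protocol 1.15.7.1** analyses AEs that begin or worsen on treatment in subjects dosed after randomisation. It treats AEs recorded before the first dose, or in the run-in, as medical history.
- **Protocol 1.12.17 and 1.12.18** place abnormal physical and ocular findings between V01 and V02 in medical history, and refer later findings to 1.16.
- **SAP 7.2**: "An AE will be considered a treatment-emergent adverse event (TEAE) if it starts on or after the reference start date". It also counts an event that began earlier but worsened from that date, up to 28 days after the last dose. The reference start date is the first dose after the run-in (SAP 4.2).
- **SAP 5.4** lists medical history with start date, end date and whether the condition was ongoing at screening.

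**The concern.** The two sentences in 1.16.1 should divide all events between them without overlap, and they do not. A new symptom at Month 6 with no link to a study procedure is an AE by the first sentence and medical history by the second. A reaction to a screening procedure also meets both.

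This matters because classification happens at the site. Under 1.16.1.1 the study team decides whether a health concern is an AE and only then enters it on the AE log. An SAE is defined in 1.16.3 as a kind of AE, and the 24-hour report in 1.16.3.1 follows from that status. SAP 7.2 classifies only what has been entered as an AE. The SAP's precedence over the protocol's statistical sections cannot recover an event that was never logged as one. Safety and tolerability are stated objectives, in subjects aged 60 or over followed for two years.

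**Working it through.** The plan gives no figure to reproduce, so the check is logical. Let A mean that the event occurs after V02, and P that it is due to a protocol procedure.

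- First sentence: AE = A or P.
- Its complement, which medical history should be: (not A) and (not P).
- Second sentence as written: medical history = (not A) or (not P).

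| Event | First sentence | Second sentence as written | Second sentence with 'and' |
|---|---|---|---|
| After V02, procedure-caused | AE | – | – |
| After V02, not procedure-caused | AE | medical history | – |
| Before V02, procedure-caused | AE | medical history | – |
| Before V02, not procedure-caused | – | medical history | medical history |

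As written, 2 of 4 cells receive both labels. With 'and', 0 of 4 do, and each cell receives exactly one.

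**After V02, not procedure-caused.** This cell holds the ordinary on-treatment events, including any possible drug reaction. The rest of the current text treats them as AEs:

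- the examples in 1.16.1 include "A subject-reported new symptom, injury, or disease";
- the CNV section, 1.16.1.3, says "Development of CNV in an eye that has no history of CNV should be recorded as AE";
- 1.16.1.6 and 1.16.1.7 make clinically significant laboratory, vital-sign and ECG abnormalities AEs;
- 1.16.1.12 grades every AE for relation to study drug, from unrelated to definite, which would have little use if only procedure-caused events qualified;
- 1.15.7.1 and SAP 7.2 use timing alone.

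**Before V02, procedure-caused.** Here the documents disagree even after the one-word change. Fluorescein angiography is required at V01 (1.12.24), so a reaction to it is a concrete case. The corrected 1.16.1 would make it an AE. Section 1.15.7.1 would still place it in medical history because it was recorded before the first dose, and 1.12.17 and 1.12.18 do the same for examination findings. Section 1.16.1.4 also uses a cut by time only. If the reaction resolves before Day 1, it is outside the SAP 7.2 TEAE definition as well.

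**Timing of any correction.** SAP 3.1 reports 200 subjects randomised, and SAP 3.2 takes 80% as having completed: 0.80 × 200 = 160. Most of the recording has therefore been done under the current wording.

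**The case against.** The strongest reply is that this is a drafting slip that no sensible site would follow. The sentence immediately before it is the operative definition, and it states that drug causation is not required. The examples, the CNV rule, the laboratory and ECG rules, the causality scale and both analysis rules point the same way. Protocol 1.5.3 also tells investigators to ask the sponsor about inconsistencies and to document the answer. Most of this stands, and it is why the point is limited to a contradiction. What it does not remove is the recording-stage risk: 1.5.3 helps only a site that notices the conflict.

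A reader might infer more, in three ways that the documents do not support.

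- *That the definition files nearly every post-randomisation event outside the AE data.* Only the second sentence read alone does so; the first sentence and the provisions listed above keep those events in.
- *That 1.16.1.4 opens a second route out of the AE data.* It covers only preexisting conditions that come to light during treatment, and it requires worsening after the first dose, or new clinically significant findings, to be recorded as AEs.
- *That misfiled events could never reach expedited reporting or the safety committee.* Section 1.16.3 counts death during participation as serious whatever its cause, 1.15.3 lets the committee request further data, and the SAP 5.4 listing would show a medical-history entry with an on-treatment start date.

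**Conclusion.** The AE definition in Protocol 1.16.1 is internally contradictory and should be corrected. The contradiction covers 2 of the 4 combinations of timing and procedure cause, one of which contains the ordinary on-treatment events. The consequence is possible under-recording at any site that applied the second sentence literally. The documents give no means of estimating how many events, if any, were affected.

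This rests on two assumptions. The first sentence and the time-based provisions are taken to express the intended rule, since they agree with one another and with SAP 7.2. Database lock is taken to be still ahead, as SAP 1.0 implies. The point is of moderate weight: it shows no loss of safety data, but it concerns the rule on which all later safety classification depends, and it is cheap to settle.

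**What to change.** 1. In the medical-history sentence of Protocol 1.16.1, change the first 'or', the one joining the two conditions, to 'and'. Medical history then holds only events that both precede V02 and have no procedure cause.
2. Reconcile 1.15.7.1, 1.12.17 and 1.12.18, and the time-only wording in 1.16.1.4, so that a procedure-caused event during screening or run-in has one stated category. State where such events are reported, since SAP 7.2 does not count them as treatment-emergent unless they worsen later.
3. Before database lock and without treatment codes, review the SAP 5.4 medical-history listing. Select entries that start on or after the reference start date, and run-in entries linked to a study procedure. Include missing or partial start dates that could fall in either group, because the date rules in SAP 4.6.1 cover AEs and medications only. Query whether each should be an AE, and document the outcome.

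Step 3 is the one that can still change the safety tables. Steps 1 and 2 now serve mainly the record, the remaining follow-up and any extension. The cost is one word, a short alignment of the related sections and a small number of site queries.

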#### Examples of AE:

- Observed by study team:
  - o A clinically-significant abnormality in physical or ocular examinations
  - o A clinically-significant finding in ECG, vital signs
- Reported by subject:
  - o A subject-reported new symptom, injury, or disease
  - o A preexisting condition that has worsened (increased in severity, frequency or pattern), unless judged by the investigator as consistent with the natural progression of the preexisting condition.
- Measured in clinical lab:
  - o Deterioration in a laboratory value or other clinical test associated with symptoms or leads to a change in study treatment or concomitant medication (See section [1.16.1.6](#)).

#### *1.16.1.1 Collection and Documentation of Adverse Events*

Collection of AE should occur according to the events table (Section [1.2](#)). During all instances of communication with subject, including phone calls or other forms of communication, study staff shall inquire about health-related concerns through non-directive, non-leading questions. Examples of non-directive questions include the following:

“How have you felt since your last visit / since we last spoke?”

“Have you had any new concerns or changes in your health since you were last here / since we last spoke?”

Study team should then determine if such concerns are AEs and if so list AEs on the AE log, and PI should determine if an unscheduled safety visit or a referral to a different physician is warranted (See section [1.12.12](#)). AE or health-related concerns may also be spontaneously reported by subjects between visits or during visits while undergoing physical or ocular examination, ECG, blood draw, or other assessments.

Follow-up monitoring of AEs: Study team should follow each AE until the event has resolved to baseline grade or better, the event is assessed as stable, the patient is lost to follow-up, or the patient withdraws

consent. Every effort should be made to follow all AEs or SAEs considered to be possibly-related or related to study drug, until a final outcome can be determined. After a subject discontinues participation, study team should follow AEs according to [1.16.1.5](#).

**Documentation of AE:** Information on AEs should be documented in source documents, with sufficient details and notes to allow adequate understanding of the AE dates, status, clinical diagnosis, signs, symptoms, body part involved.

**Recording and updates:** Study team shall avoid colloquialisms and abbreviations in the AE description. Not all information regarding the AE may be available at the time the AE is detected or documented (including for example: definitive diagnosis, dates of AE, AE outcome, action taken, or causality to study treatment). Such information should be recorded as soon as it becomes available. See section [1.16](#) for details.

**Description of the event:** When recording AEs, study team should use correct medical terminology and concepts. AEs may fit into different categories based on available information:

**Definitive diagnosis:** If a clinical diagnosis is known and confirmed by investigator, record the diagnosis. Study team may also list signs and symptoms in a side “note.” (eg: record “hepatitis” if known to be the diagnosis rather than “jaundice, asterixis, and elevated transaminases”).

**Definitive diagnosis along with signs/symptoms not normally associated with the diagnosis:** If any signs or symptoms are not normally associated with the definitive diagnosis, study team shall list these signs/symptoms in separate AEs.

**Presumed/Provisional diagnosis:** If at the time of report, a diagnosis is unknown or unsure, study team shall record in a single AE, the provisional diagnosis as well as the reported signs/symptoms (eg: “presumed influenza with low grade fever”). If a clinical diagnosis becomes later known and confirmed by investigator, AE should be updated to indicate the definitive diagnosis.

**Constellation of signs or symptoms that cannot be characterized as a single diagnosis:** study team shall record each individual sign and/or symptom as its own event. These AEs should be updated if a diagnosis is later determined

**AEs occurring secondary to a primary event:** in general, in case of a cascade of events or clinical sequelae, study team shall record the primary cause, with the exception of severe or serious secondary events, or medically significant AEs occurring at separate points in time, which shall be recorded separately. For example:

- *If vomiting results in mild dehydration with no additional treatment, only vomiting should be recorded.*
- *If vomiting results in severe dehydration, both events should be recorded separately*
- *If dizziness leads to a fall and consequent fracture, all three events should be recorded separately*

**Recording of AE Parameters:** For each AE, study team should record:

- Verbatim description of the event (including either *definitive* diagnosis with signs/symptoms in notes, or a *provisional* diagnosis, along with signs and symptoms in the verbatim description, when a definitive diagnosis is not known)
- Start Date/Time
- Is the AE ongoing or not?
- End Date/Time
- Is the AE “serious” or “not serious” (see section [1.16.3](#))
- AE severity (see section [1.16.1.11](#))

- Frequency/Pattern (Single event, Intermittent, continuous)
- Action taken related with study treatment (see section 1.16.1.13)
- Action taken unrelated with study treatment (see section 1.16.1.15)
- AE outcome (see section 1.16.1.14)
- AE causality to study treatment (see section 1.16.1.12)
- Did AE cause subject to withdraw from the study?

*1.16.1.2 Worsening of Geographic Atrophy and AE*  
Events consistent with expected pattern of progression of Geographic Atrophy or AMD should not be recorded as AEs.

Worsening of Geographic Atrophy. Medical occurrences or symptoms of deterioration anticipated as part of normal progression of GA should be recorded as AE only if judged by investigator to have unexpectedly worsened in severity or frequency or changed in nature during the study. When recording an unanticipated worsening of GA, study team should emphasize that condition has unexpectedly changed by including applicable descriptors (eg: “accelerated GA”).

*1.16.1.3 Presence, Development and Worsening of CNV in either eye*

Subjects with Geographic Atrophy are at risk of developing CNV, with a higher risk if one eye has concurrent or a history of CNV. As such:

- Clinical changes in pre-existing CNV consistent with expected progression of CNV should not be recorded as AEs.
- Clinical changes in pre-existing CNV inconsistent with expected progression of CNV should be recorded as AEs.
- Development of CNV in an eye that has no history of CNV should be recorded as AE.

There is no expectation that the study drug would aggravate or accelerate CNV in a subject. As such, treatment with the study drug should continue in case of CNV-related AE.

*1.16.1.4 Preexisting Condition(s) and AE*

Preexisting condition known or discovered at screening or during the run-in period. A preexisting condition is one present prior to or identified during the screening or run-in period, before the first study drug is administered (V02). *Preexisting conditions should be recorded as “Medical History.”*

Clinically-significant abnormality during the screening period. Any clinically-significant abnormality (eg: lab value, ECG, physical exam, etc.) identified during screening or run-in period should be recorded as part of the subject’s medical history.

Preexisting condition discovered during the treatment period. Because patients may sometimes fail to report, or the investigator may fail to detect all preexisting conditions during the screening period, preexisting conditions discovered during the treatment period shall also be recorded as part of the subject’s medical history.

Changes in a condition marked as preexisting condition (other than AMD/CNV or Geographic Atrophy). During the treatment period, a condition previously recorded as a preexisting condition should be recorded as an AE if the frequency, intensity, or the character of the condition worsens after the administration of the first dose of study drug, or if any new clinically-significant findings/abnormalities that meet the

definition of an AE are observed. Progression of the disease consistent with the disease natural history shall not be considered an AE.

